
 Awareness (Receipt) after February 2020 	
≥80% of HCPs reporting that they received 4 out of the 4 (100%) aRMM materials⁵ in all countries, except for Germany
 
≥80% of HCPs reporting that they received 3 out of the 3 (100%) aRMM materials⁶ in Germany
	
≥80% of HCPs reporting that they received 4 out of the 4 (100%) aRMM materials⁵ in all countries, except for Germany
 
≥80% of HCPs reporting that they received 3 out of the 3 (100%) aRMM materials⁶ in Germany

 Knowledge 	
≥80% of HCPs correctly answering ≥14 out of 18 (≥78% [or approximately 80%]) of the knowledge questions
	
≥80% of HCPs correctly answering ≥16 out of 20 (≥80%) of the knowledge questions

 Adherence 	
≥80% of HCPs providing desirable responses for ≥14 out of 17 (≥82% [or approximately 80%]) of the adherence questions
	
≥80% of HCPs providing desirable responses for ≥14 out of 17 (≥82% [or approximately 80%]) of the adherence questions

Note: The measures of effectiveness in each of the 4 domains listed above will be calculated variables.

⁵ The 4 aRMM materials include: the Xeljanz Prescriber Brochure, the Xeljanz Prescriber Treatment Initiation Checklist, the Xeljanz Prescriber Treatment Maintenance Checklist, and the Xeljanz Patient Alert Card. As the Xeljanz Prescriber Website is a repository for the aRMM materials, rather than a tool in and of itself, awareness of the Xeljanz Prescriber Website will not be considered when evaluating the effectiveness of the entire aRMM program.

⁶ The 3 aRMM materials include: the Xeljanz Prescriber Brochure, the Xeljanz Prescriber Treatment Initiation and Maintenance Checklist, and the Xeljanz Patient Alert Card. As the Xeljanz Prescriber Website is a repository for the aRMM materials, rather than a tool in and of itself, awareness of the Xeljanz Prescriber Website will not be considered when evaluating the effectiveness of the entire aRMM program.

6. Attitude toward the aRMM materials (i.e., how useful the HCPs find the various aRMM materials in their practice).

- There are 5 survey questions (1 question for each of the aRMM materials plus 1 question for the Xeljanz Prescriber Website) that ascertain HCPs' attitudes towards the aRMM materials, except for Germany, which has 4 questions.

7. Source of HCPs' information on the safety of Xeljanz.

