- There is 1 survey question that asks HCPs to identify their primary source of safety and prescribing information regarding Xeljanz from a list of pre-populated choices.

Response rate, eligibility rate, completion rate. The HCPs' participation in the survey study will be examined by calculating the following mutually exclusive categories of HCPs

Survey administration statistics

- The number of invitations issued (I);
- The number of invitations returned as undeliverable (R)
- The number of respondents screened for participation (S);
 - **Survey response rate** = $S/(I-R)$;
- The number of respondents eligible for participation (E);
 - **Eligibility rate** = E/S ;
- The number of eligible respondents who completed the survey (C);
 - **Completion rate** = C/E ;

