#	Key Risk Message	Total Number of Survey Questions (counting each individual response option as a separate question)	Number of Knowledge Questions	Number of Adherence Questions
1	Use in special populations	4	4	0
2	Combination with biologics and/or other potent immunosuppressants	1	1	0
3	Lab monitoring	9	4	5
4	Serious infections	5	3	2

Table 3. Key Risk Messages and Associated Number of RA/PsA Survey Questions, Stratified by Type of Question (i.e., Knowledge or Adherence)

#	Key Risk Message	Total Number of Survey Questions (counting each individual response option as a separate question)	Number of Knowledge Questions	Number of Adherence Questions
5	Viral reactivation and vaccination	4	2	2
6	Malignancies	2	1	1
7	Gastrointestinal perforations	1	1	0
8	Venous thromboembolism	3	2	1
9	Patient counseling	4	0	4 ^a
N/A	Other ^b	2	0	2 ^b
	TOTAL	35	18	17

Abbreviations: N/A = not applicable; PsA = psoriatic arthritis; RA = rheumatoid arthritis.

- a. Survey question 11a. In your clinical practice, how frequently do you “[d]istribute the patient alert card to patients” is counted as both an adherence and a utilisation (Table 2) question.
- b. Survey questions 7a, “Does this patient have gastroesophageal reflux disease (GORD/GERD)?”, and 7d, “Does this patient have a history of hyperthyroidism?”, are wrong answer options that do not correspond to any of the key risk messages.

As shown in Table 4, each key risk message has at least 1 corresponding UC survey question. There is a total of 37 survey questions related to the key risk messages. Twenty of these 37 questions are **knowledge questions** and 17 of the 37 are **adherence questions**. For survey questions consisting of several response options, each individual response option is counted as a separate question since they can be viewed as distinct sub-messages pertaining to the key risk messages.

Table 4. Key Risk Messages and Associated Number of UC Survey Questions, Stratified by Type of Question (i.e., Knowledge or Adherence)

#	Key Risk Message	Total Number of Survey Questions (counting each individual response option as a separate question)	Number of Knowledge Questions	Number of Adherence Questions
1	Use in special populations	5	5	0
2	Combination with biologics and/or other potent immunosuppressants	1	1	0
3	Lab monitoring	10	5	5
4	Serious infections	5	3	2

Table 4. Key Risk Messages and Associated Number of UC Survey Questions, Stratified by Type of Question (i.e., Knowledge or Adherence)

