8.7.3. Primary Analysis: Study Objective 2—Knowledge of Key Risk Messages

	RA/PsA Survey	UC Survey
Per question analysis	The number and proportion of HCPs providing a correct answer for each of the 18 knowledge questions will be reported.	The number and proportion of HCPs providing a correct answer for each of the 20 knowledge questions will be reported.
Overall	The number and proportion of HCPs providing correct answers to <13, 13-14, 15-16, 17, and 18 out of the 18 knowledge questions will be reported. The number of correct answers to the 18 knowledge questions per HCP	The number and proportion of HCPs providing correct answers to <14, 14-15, 16-17, 18-19, and 20 out of the 20 knowledge questions will be reported. The number of correct answers to the 20 knowledge questions per

090177e199ebc283\Approved\Approved On: 11-Apr-2022 22:32 (GMT)

	RA/PsA Survey	UC Survey
	will also be summarized continuously using mean, SD, median, range, and IQR.	HCP will also be summarized continuously using mean, SD, median, range, and IQR.

8.7.4. Primary Analysis: Study Objective 3-Adherence to the Risk Minimisation Practices Recommended in the aRMM Materials

	RA/PsA survey	UC survey
Per question analysis	The number and proportion of HCPs providing a desirable response for each of the 17 adherence questions will be reported.	The number and proportion of HCPs providing a desirable response for each of the 17 adherence questions will be reported.
Overall	The number and proportion of HCPs providing desirable responses to <12, 12-13, 14-15, 16, and 17 out of the 17 adherence questions will be reported. The number of desirable responses to the 17 adherence questions per HCP will also be summarized continuously using mean, SD, median, range, and IQR.	The number and proportion of HCPs providing desirable responses to <12, 12-13, 14-15, 16, and 17 out of the 17 adherence questions will be reported. The number of desirable responses to the 17 adherence questions per HCP will also be summarized continuously using mean, SD, median, range, and IQR.

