Select the best response for each scenario: “I would discontinue tofacitinib,” “I would interrupt dosing,” “I would lower the dose,” OR “I would take no action.”

		I would discontinue tofacitinib	I would interrupt dosing	I would lower the dose	I would take no action
a	The patient’s neutrophil count is less than 0.50 cells x 10 ⁹ /L. This is confirmed by repeat testing.	•	○	○	○
b	The patient’s lymphocyte count is between 0.50-0.75 cells x 10 ⁹ /L. This is confirmed by repeat testing.	○	•	○	○
c	The patient develops a serious infection, an opportunistic infection or sepsis.	○	•	○	○
d	The patient develops severe hepatic impairment (Child Pugh C).	•	○	○	○
e	The patient’s haemoglobin level is <8 g/dl. This is confirmed by repeat testing.	○	•	○	○
f	The patient has a suspected venous thromboembolism (VTE).	•	○	○	○

Data: Single punch per row.

Data: Answer options will be displayed in a random order for each survey participant.

Answer: The black circles indicate a desired response.

090177e199ebc283\Approved\Approved On: 11-Apr-2022 22:32 (GMT)

[QUESTIONS ABOUT ADHERENCE TO KEY RISK MESSAGES FOR TOFACITINIB]

[QUESTION APPLIES TO ALL COUNTRIES]

Q11. In your clinical practice, how frequently do you perform each of these activities when **initiating treatment** with tofacitinib? Please select the best response: “Always,” “Sometimes,” or “Never”.

		Always	Sometimes	Never
a	Give the tofacitinib patient alert card to the patient.	•	•	○
b	Advise the patient to inform you immediately if they experience any of the symptoms on the tofacitinib patient alert card.	•	•	○
c	Advise patients to carry the tofacitinib patient alert card with them, particularly when they visit a doctor, a hospital, or Accident and Emergency.	•	•	○
d	Discuss the signs and symptoms of venous thromboembolism (VTE) with the patient.	•	•	○

Data: Multiple punch.

Answer: The black circles indicate a desired response.

090177e199ebc283\Approved\Approved On: 11-Apr-2022 22:32 (GMT)

[SOURCE OF HCPs' INFORMATION ON THE SAFETY OF TOFACITINIB]

[QUESTION APPLIES TO ALL COUNTRIES]

The final set of questions asks about sources of information on tofacitinib.

Q12. Which of the following is your **primary source** of safety and prescribing information for tofacitinib? Please select one.

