Q10. In your clinical practice, which actions would you take when faced with the following scenarios during tofacitinib **treatment maintenance**? **Assume in all scenarios that the patient is receiving tofacitinib 5 mg twice daily unless otherwise noted.**

Select the best response for each scenario: “I would discontinue tofacitinib,” “I would interrupt dosing,” “I would lower the dose,” OR “I would take no action.”

		I would discontinue tofacitinib	I would interrupt dosing	I would lower the dose	I would take no action
a	The patient’s neutrophil count is less than 0.50 cells x 10 ⁹ /L. This is confirmed by repeat testing.	•			
b	The patient’s lymphocyte count is between 0.50-0.75 cells x 10 ⁹ /L. This is confirmed by repeat testing.		•		
c	The patient’s lymphocyte count is between 0.50-0.75 cells x 10 ⁹ /L. This is confirmed by repeat testing. The patient is receiving tofacitinib 10 mg twice daily for ulcerative colitis.			•	
d	The patient develops a serious		•		

090177e199ebc283\Approved\Approved On: 11-Apr-2022 22:32 (GMT)

		I would discontinue tofacitinib	I would interrupt dosing	I would lower the dose	I would take no action
	infection, an opportunistic infection or sepsis.				
e	The patient develops severe renal impairment (creatinine clearance <30 mL/min) and is taking tofacitinib 10 mg twice daily for ulcerative colitis.				
f	The patient develops severe hepatic impairment (Child Pugh C).				
g	The patient's haemoglobin level is <8 g/dl. This is confirmed by repeat testing.				
h	The patient has a suspected venous thromboembolism (VTE).				

Data: Multiple punch.

Data: Answer options will be displayed in a random order for each survey participant.

Answer: The black circles indicate a desired response.

[QUESTIONS ABOUT ADHERENCE TO KEY RISK MESSAGES FOR TOFACITINIB]

[QUESTION APPLIES TO ALL COUNTRIES]

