Q11. In your clinical practice, how frequently do you perform each of these activities when **initiating treatment** with tofacitinib? Please select the best response: “Always,” “Sometimes,” or “Never”.

		Always	Sometimes	Never
a	Give the tofacitinib patient alert card to the patient.	•	•	○
b	Advise the patient to inform you immediately if they experience any of the symptoms on the tofacitinib patient alert card.	•	•	○
c	Advise patients to carry the tofacitinib patient alert card with them, particularly when they visit a doctor, a hospital, or Accident and Emergency.	•	•	○
d	Discuss the signs and symptoms of venous thromboembolism (VTE) with the patient.	•	•	○

Data: Multiple punch.

Answer: The black circles indicate a desired response.

[SOURCE OF HCPs' INFORMATION ON THE SAFETY OF TOFACITINIB]

[QUESTION APPLIES TO ALL COUNTRIES, EXCEPT FOR GERMANY]

The final set of questions asks about sources of information on tofacitinib.

Q12. Which of the following is your **primary source** of safety and prescribing information for tofacitinib? Please select one.

a	Educational materials (documents designed for the patient and the physician, such as the tofacitinib prescriber brochure, the prescriber initiation and maintenance checklists, and the patient alert card)	
b	Summary of Product Characteristics (Label)	
c	National Health Authority website/National formulary website	
d	Pharmaceutical company website	
e	Do not know/recall the source	
f	Other	

Data: Single punch.

Data: Answer options will be displayed in a random order for each survey participant, with an exception for "Do not know" and "Other" – always keep these as the last two options.

[QUESTIONS ABOUT AWARENESS (RECEIPT) AND UTILISATION OF TOFACITINIB aRMM MATERIALS]

[QUESTION APPLIES TO ALL COUNTRIES]

Q13.1a. Have you ever received a **prescriber brochure for tofacitinib**? Please select one.

- Yes
- No
- I don't remember

Data: Single punch.

[QUESTION APPLIES TO ALL COUNTRIES EXCEPT POLAND]

Q13.1b. The **prescriber brochure for tofacitinib** was updated in 2020. Did you receive a prescriber brochure after February 2020? Please select one.

- Yes
- No
- I don't remember

Data: Single punch.
Ask only if Yes in Q13.1a.

[QUESTION APPLIES TO POLAND ONLY]

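### UC Q10 is programmed for several ticks per row although its stem, its key and the RA/PsA version call for one, and UC Q12 is tagged as not asked in Germany against the rest of the protocol

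*Protocol*

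**What the plan says.** **Q10.** UC Q10 (Appendix 2) lists eight maintenance-phase scenarios, a to h, each with four possible actions joined by OR. The stem reads "Select the best response for each scenario", and one response per row is marked as desired. The programming line beneath it is "Data: Multiple punch". The same type of question in the RA/PsA questionnaire (Appendix 1, Q10) carries "Data: Single punch per row", as do UC Q6 to Q9.

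Appendix 4 classes all eight UC Q10 items as knowledge items with a single desired response. Section 8.3.1 counts the scored items: "Twenty of these 37 questions are knowledge questions and 17 of the 37 are adherence questions". Section 8.3 sets the UC knowledge effectiveness criterion as "≥80% of HCPs correctly answering ≥16 out of 20 (≥80%) of the knowledge questions", and Section 8.7.3 adds "The number and proportion of HCPs providing a correct answer for each of the 20 knowledge questions will be reported".

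**Q12.** This question on the primary information source is tagged in Appendix 2 "QUESTION APPLIES TO ALL COUNTRIES, EXCEPT FOR GERMANY". Appendix 1 and the Appendix 4 crosswalk tag it for every country. Section 8.3, item 7, says "There is 1 survey question that asks HCPs to identify their primary source of safety and prescribing information regarding Xeljanz" without a country exception, and Section 8.7.7 analyses it without one.

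**The concern.** The programming line tells whoever builds the survey what a respondent may do. Here it permits something that the stem, the key and the scoring do not provide for. If a prescriber ticks two actions in one row, the protocol does not say whether that row is correct, incorrect or excluded. The gap covers 8 of the 20 items that decide whether UC knowledge, one of the effectiveness domains, meets its target. It also affects the per-question results for those eight items.

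The Q12 tag is a smaller, separate matter. If it was followed, an outcome described as covering all eight countries would rest on seven in the UC survey only, and nothing in the analysis sections would tell the reader so.

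**Working it through.** **1. Reproduce the count of 20.** UC knowledge items in Appendix 4, by key risk message:

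- 1: Q6a, Q6b, Q6c, Q10e, Q10f (5)
- 2: Q7a (1)
- 3: Q7d, Q10a, Q10b, Q10c, Q10g (5)
- 4: Q6d, Q7g, Q10d (3)
- 5: Q7c, Q7f (2)
- 6: Q7b (1)
- 7: Q7e (1)
- 8: Q7h, Q10h (2)

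The sum is 5 + 1 + 5 + 3 + 2 + 1 + 1 + 2 = 20, which matches Table 4.

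**2. Share from Q10.** 2 + 4 + 1 + 1 = 8 items, and 8/20 = 40%. The other items are Q6 (4) and Q7 (8), so 12. Since 16 − 12 = 4, no respondent can meet the threshold without at least four Q10 rows counted correct. The RA/PsA survey has 18 knowledge items, 6 of them from Q10, and those are limited to one choice per row.

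**3. Does the programming term mean multi-select?** In Appendix 1, S3 carries the same term and tells respondents to select every diagnosis that applies. Read consistently, a programmer would allow several ticks in UC Q10.

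**4. How much the scoring rule could matter (illustration; all rates are assumed).** Let items be independent, each correct with probability p, and let a share m of otherwise correct Q10 rows carry a second tick. If such rows still count, the score is Bin(20, p). If they do not, it is Bin(12, p) + Bin(8, p(1 − m)). P(score ≥ 16):

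| p | second tick still counts | not correct, m = 5% | not correct, m = 10% | not correct, m = 20% |
|---|---|---|---|---|
| 0.80 | 0.63 | 0.56 | 0.49 | 0.36 |
| 0.85 | 0.83 | 0.77 | 0.70 | 0.55 |
| 0.90 | 0.96 | 0.92 | 0.88 | 0.75 |

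At p = 0.85 the result lies above or below the 80% target according to the scoring rule alone, even at m = 5%. At p = 0.80 it misses under both rules. At p = 0.90 it passes under both rules unless m reaches 20%. The model adds second ticks only to rows that were already right. A lenient rule could also credit rows where the first choice was wrong, which would raise the score above its single-choice value.

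**5. Germany in the UC sampling frame.** Appendix 5 lists 4,350 gastroenterologists in Germany out of 17,452 in total: 4,350/17,452 = 24.9%.

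**6. What can still be changed.** Version 3.0 is dated 28 March 2022. In Table 1, seven of the eight country windows end by 1 March 2022. Only Romania's tentative window, to 25 April 2022, extends beyond the version date.

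**The case against.** The strongest reply is that this is a copy error with no effect. Everything else in UC Q10 points to a single choice: the stem, the OR between the actions, the radio-style cells and the one-answer key. The same programming line sits under Q11, a plainly exclusive Always/Sometimes/Never grid, in both surveys, so the term is used loosely. Section 8.8.1 has the programming reviewed by quality control and simulated users, and Section 8.8.2 adds real-time answer checks. The protocol shows an instruction and not what respondents saw, and a scoring rule may sit in the SAP, which is not shown. All of this stands. It makes a copy error likely and the correction easy, but it does not remove the conflict or show which setting was fielded.

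A reader might infer that UC knowledge will be inflated. The documents do not support that, because no section credits a row holding the keyed tick plus another, and scoring such rows as not correct would lower the result.

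A reader might also note that ticking the same two actions (discontinue and interrupt) in every row would capture 6 of the 8 keyed responses. That is arithmetically true, but it supposes respondents who ignore the stem throughout. Loss of comparability with RA/PsA carries little weight: Section 8.7.1 analyses the two surveys separately, and they already differ in item count and threshold.

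Q11 should not be counted as a scoring problem of the same kind. Its line is the same in both surveys, and Always and Sometimes are both keyed desirable, so ticking both does not change the score.

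**Conclusion.** Both contradictions are in the text.

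- **Q10** carries the weight. It makes up 8 of 20 scored items (40%) in an effectiveness criterion that cannot be met without it, and the status of a multi-ticked row is undefined in the protocol. The direction and size of any bias are unknown. They depend on whether several ticks were possible, how often they occurred and how they are scored. The illustration rests on assumed rates and shows only that the choice of rule can decide the result when performance is near the target.
- **Q12** is minor. It feeds a secondary descriptive outcome, reported without confidence intervals and outside every effectiveness domain. The 24.9% is Germany's share of listed gastroenterologists and should not be read as a share of completed surveys. Section 8.5 expects low response where no honorarium is offered, and Germany is one of those countries.

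The point concerns programming and scoring only. It takes no view on the clinical actions in the key.

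**What to change.** 1. In Appendix 2, change the UC Q10 line to one punch per row and tag Q12 for all countries. Apply both wherever fielding is still open.
2. For countries whose windows have closed, verify from the fielded survey whether UC Q10 accepted several ticks and whether Germany was asked Q12. State the answer in the report.
3. If several ticks were possible, state before analysis that a UC Q10 row with more than one tick is scored not correct, since the stem asked for one best response. Report how many such rows occurred.
4. If Germany was not asked Q12, report the UC information-source outcome as excluding Germany.
5. Align the Q11 programming line in both surveys for consistency, but do not apply the rule in step 3 to rows with both Always and Sometimes ticked.

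The cost is small: two corrected lines, a check of the fielded settings, a one-sentence scoring rule and, if needed, a note in the report. The sample size does not change. For the seven countries with closed windows, reprogramming is no longer possible under the dates in Table 1, so the rule and the note do the work there.

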Appendix 5. Number of Anticipated HCPs* in the OneKey Database, by Country and by Specialty

	Rheumatology	3.5% Response Rate	1.7% Response Rate	Dermatology	3.5% Response Rate	1.7% Response Rate	Gastroenterology	3.5% Response Rate	1.7% Response Rate
France	2,847	100	48	4,094	143	70	4,367	153	74
Germany	1,478	52	25	7,841	274	133	4,350	152	74
Netherlands	397	14	7	761	27	13	762	27	13
Poland	691	24	12	2,308	81	39	502	18	9
Romania	367	13	6	1,027	36	17	566	20	10
Spain	1,480	52	25	2,686	94	46	3,842	134	65
Sweden	370	13	6	589	21	10	357	12	6
United Kingdom	1,502	53	26	1,793	63	30	2,706	95	46
Total	9,132	321	155	21,099	739	358	17,452	611	297

* "HCPs" refers to HCPs in the OneKey database whose *primary* specialty is recorded as either dermatology, gastroenterology, or rheumatology (versus any specialty). These counts represent the highest and most relevant possible number of specialists in the OneKey database to be invited to participate in the HCP survey. A proportion of the specialists represented in this table are expected to be eligible to prescribe Xeljanz and/or to treat their patients with Xeljanz.

Document Approval Record

Document Name: A3921334_PROTOCOL AMENDMENT 2_XELJZANZ_HCP_SURVEY
_28MAR2022_CLEAN

Document Title: A3921334_PROTOCOL AMENDMENT 2_XELJZANZ_HCP_SURVEY
_28MAR2022_CLEAN

Signed By:	Date(GMT)	Signing Capacity
[name]	11-Apr-2022 16:48:51	Manager Approval
[name]	11-Apr-2022 22:32:57	EUQPPV Approval
